## A2. CONCEPTUAL MODEL: PATIENT-CENTERED ACCESS TO MENTAL HEALTH CARE

Using both theory and empirical evidence, the focus of this CDA will be to: (1) identify risk profiles associated with depression treatment engagement, to test prediction models and select patients for the proposed intervention; (2) design an eHealth intervention program using technology driven self-monitoring; and (3) conduct a formative evaluation and pilot this eHealth intervention.

First, we will identify possible patient profiles or phenotypes associated with treatment engagement. Profiles will be constructed using structured data and will be used to calculate risk scores associated with patient lack of engagement in treatment for depression (Aim 1). Guiding the development of a pre-treatment intervention (Aim 2) will be Levesque's Framework which proposes that patient's ability to **engage** is at the core of successful health care consequences (i.e., outcomes). Therefore, the focus will be on the development of an intervention that will provide patients the mechanism to initiate treatment, and then ideally remain actively engaged with their own care, which prior work has shown to increase adherence and improve treatment outcomes (e.g., Guo et. al, 2015). This will be done via active self-monitoring and specific labeling of depression symptoms, as well as via emotional and practical support. Based on this framework, the process by which behavior change about treatment is activated is by helping patients more clearly identify health care needs (i.e., via symptom monitoring) help rectify perception of needs (by providing feedback on symptoms, whether they are elevated and a provider should be contacted), helping with care seeking and reaching (i.e., sending provider contact information and sending reminders).

Formative methods will be used to evaluate and pilot this process (Aim 3) in preparation for a future efficacy/effectiveness RCT (IIR developed in year 3). Our study focuses on solidifying engagement in care for those patients whose needs have been identified by provider and have been referred for care. Focusing on this segment of the patient population with mental health care needs ensures that our sample already meets basic

[figure not shown]

Figure 1. Conceptual framework.

steps in accessing care. Based on our conceptual framework we hope to systematically and progressively reach patients with more complex barriers to care in future work. The proposed CDA sets the ground work for such future studies (see Future Research Projects section).


**Daily assessments of functioning among depressed individuals (2014 - present):** Starting in graduate school, I have become interested in daily life functioning of individuals with depression. Papers stemming from my dissertation and two additional studies with collaborators used data from ecological momentary assessments or daily diary methodology that prompted participants through their own cellphones to report on daily events, symptoms, or emotions throughout the day. In the three studies I have conducted or reported on, participants were prompted anywhere from 1 to 10 times a day for 3 to 7 days. Although there was some variability in assessment completion rate among depressed versus healthy individuals, generally differences were not statistically significant suggesting that this manner of assessment is acceptable to samples of individuals with psychopathology. Relevance to the proposed CDA: Completion of daily assessments is highly feasible even among individuals with verified depression diagnoses. Furthermore, these studies provided ample experience with programming daily diary protocols, recruiting patients for daily diary studies, collecting data using this methodology and analyzing multilevel data. My dissertation alone provided the requisite skills to conduct complex studies as it was a two-step study involving an experimental laboratory protocol and daily diary study.

**Phenotypes associated with depression and depression course (2009-present):** Over the course of my graduate training I was involved in two NIH funded studies led by my long standing mentor and consultant on the current CDA, [name]: 1. Vagal Fluctuation as a Predictor of Current and Future Depression; 2. Biobehavioral Inflexibility and Risk for Juvenile Onset Depression. Subprojects that I contributed to or led, showed differences between current and remitted depression in how it impacts emotional reactivity (Salomon et al, 2013). In a secondary analysis I led on currently depressed individuals I found that patients' engagement with sad stimuli predicted symptomatic improvement over 30 weeks ([name] et al, 2016). In fact, in a recent manuscript we discuss findings from the national MIDUS study suggesting that depressed individuals that retain some level of wellbeing during a depressed state are more likely to experience high functioning 10 years later ([name],..., [name], et al., 2018). My most recent manuscript shows that daily affect predicts both symptomatic recovery and wellbeing in adults with depression ([name],...[name], under review). Relevance to the proposed CDA: There is observable variability among depressed individuals even during a depressed state that predicts their functioning well into the future. My role as project manager on these NIH funded studies have also provided the experience of managing changing requirements, varying regulatory needs, and managing and training the staff necessary to conduct daily tasks. My work on MIDUS will more directly support the development of the CDA as we will be using these data to compute national average levels of daily depression and mood levels. Finally, I developed the skills to perform longitudinal analyses using multilevel data.

**Barriers to behavioral change and decreasing barriers through primary care intervention (2006-2009):** Before starting graduate school, I contributed to a variety of studies investigating barriers to behavioral change among primary care patients and subsequent development of targeted interventions to facilitate health behaviors. This work suggested that primary care physicians were more amenable to integrating brief targeted interventions that did not burden care and helped facilitate behavioral change in their patients. Relevance to the proposed CDA: Primary care physicians may be supportive of adopting a system like that proposed in the current CDA. This has implications for implementation efforts in the future. This series of studies also provided knowledge and skills necessary to develop healthy collaborations with primary care physicians and other care providers in busy primary care offices, as well as intervention development skills. *I was the primary statistician on 6 publications coming out of this work.*

#### **A3b. Mentor/Consultant Research**

**[name] (Primary mentor; Measurement and health services analytics, informatics research).** [name] has been PI on multiple HSR&D funded studies using big data. He was a Site PI of the VA HSR&D Consortium for Healthcare Informatics Research (CHIR). The CHIR was comprised of a multidisciplinary group of collaborating investigators affiliated with VA sites distributed across the US. The mission of the CHIR was to improve the health of Veterans through foundational and applied informatics research. The primary purpose of the research was to advance the effective use of unstructured text and other types of clinical data in the EHR. Relevance to the proposed CDA: [name], primary mentor, will provide mentorship in the development and conduct of research using big data and machine learning protocols (Research/Training Aim 1) *in collaboration with [name] (Stage 1 Aim 1) and [name] (Stage 2 Aim 1).*

**[name] (Co-primary mentor; eHealth intervention development, electronic data collection, formative evaluation and implementation science).** [name] has had a series of projects focused on Veterans' and VA employees' experiences using VA's electronic resources (i.e. My HealtheVet, Kiosks, Mobile, Telehealth) to support national redesign efforts, uptake, and sustained use to support integrated proactive use of these tools to increase access and support care delivery, and self-care management. [name] has also had several projects funded and supported by HSR&D and QUERI to support electronic collection of patient-reported outcomes using multiple platforms (e.g. texting, secure messaging) and data management systems (e.g. Qualtrics). Finally, [name] is currently conducting a large multi-site RCT evaluating the use of a dyadic mobile/web-based intervention to help Veterans manage chronic pain and PTSD related symptoms. Relevance to the proposed CDA: [name], co-primary mentor, will provide guidance in the development and problem-solving stages of the proposed CDA with a focus on the development of Aims 2 and 3, in planning next steps for a merit award, and in planning for implementation activities for my program of research.

#### **[name] (Secondary mentor; Mental health innovation, services, and outcomes)**

[name] has conducted several intervention trials using mobile health technologies to improve and inform care for depression. For example, he developed a text-messaging intervention which sent daily text messages to individuals with depression for 3 months, conducted a VA pilot study of an automated depression monitoring program in conjunction with support from a peer specialists or family member for patients who had been psychiatrically hospitalized with a diagnosis of depression, conducted extensive inquiry into the quality of VA depression care using health system data and utilized mixed methods approaches to extend our understanding

of the barriers and facilitators to implementation of mental health services, particularly for depression. Relevance to the proposed CDA: [name], secondary mentor, will support the development of the technology driven intervention in collaboration with [name], and in understanding VA systems of care related to depression management. He will also mentor on the development of a follow-up IIR proposing an RCT in year 3.

**[name] (Consultant; symptom reporting).** [name] most recent HSR&D funded grants was a 4-year RCT to investigate the utility of a smart phone application to reduce postconcussion symptoms and improve family and community participation among Veterans with mild traumatic brain injury, through symptom self-monitoring. Relevance to the proposed CDA: [name], consultant, has extensive expertise in developing innovative interventions including by using technology to assess symptomatology among Veterans from Iraq and Afghanistan at the Tampa VA. [name] will advise in the development of the proposed technology driven intervention, patient recruitment and retention for the proposed CDA.

#### **A4. RESEARCH DESIGN AND METHODS**

*Aim 1 consists of an analysis of data extracted from the EHR to identify risk profiles (scores) and determine which patients are unlikely to engage in care for depression. These risk scores will be used to select patients for a proposed intervention that will be developed in Aim 2 and subjected to a formative evaluation in Aim 3. The intervention is technology-based and includes automated symptom assessment with emotional and practical support texts to provide interim support to Veterans referred to mental health care who are awaiting their initial mental health treatment visit.*

##### **A4a. Aim1.**

Study/Design overview: I will conduct a secondary data analysis of EHR data. This will be a retrospective cohort study to identify patient phenotypes associated with lack of treatment engagement for depression. This aim was developed based on empirical evidence and Levesque's Framework (2013) (Figure 1), which proposes that patient level factors impact health care utilization and outcomes. Our proposed analyses will focus on data available from EHRs (observed variables). Based on this framework, patient level factors may impact the process of initiating care along a continuum of identifying health care needs, perception of needs and desire for care, health care seeking, and reaching. These factors will be captured through proxy measures available in the EHRs. For example, based on the literature reviewed in the background and my own preliminary work, identification of care needs, perception of needs, and desire for care are all a function of depression severity, gender, and ethnicity, such that higher severity, female gender, and white race tend to all be associated with higher levels of perception of needs and openness to mental health care. Specifically, for this study, we plan to use the 88,456 OEF/OIF Veterans with a Patient Health Questionnaire 9 (PHQ9)  $\geq 10$  (indicative of probable depression) randomly split into sub-samples to accommodate our goals. I plan to develop Aim 1 in two related stages. (Stage 1) First, I will develop patient profiles using conventional logistic regression analysis. In this analysis, the estimated 88,456 OEF/OIF Veterans with a PHQ9  $\geq 10$  will be randomly split into development and validation sub-cohorts. Estimates extracted from the development sub-cohort will be used to compute risk scores, with ROC analysis performed to determine a presumed optimal cut-off score. These profiles and cutoff score will be evaluated for prediction accuracy on the validation sub-cohort. (Stage 2) To evaluate the results from Stage 1, patient profiles will then be developed and validated with machine learning paradigm on the 88,456 OEF/OIF Veterans with a PHQ9  $\geq 10$ . Use of this approach is based on the fact that while various characteristics have been investigated in the past in an attempt to identify patients' likelihood to use services, we have yet to apply advanced machine learning techniques to the rich data available in the EHRs to define a profile of patients at risk to not engage in mental health care for depression. Ultimately, our goal is to identify the best fitting model in terms of prediction performance and interpretation, whether by logistic regression analysis or machine learning methods. The risk scores identified in this Aim will be utilized to recruit patients for Aims 2 and 3. While the models developed for Aim 1 will be based on "observed" variables only, there may be important "unobserved" variables we are not able to include. Methods related to this potential concern are described below in the Analysis Plan section.

Table 1. List of variables extracted from electronic medical record data.

Observed Independent Variables	
Demographics	Age, gender, race/ethnicity, marital status, service connected disability.
Non-psychiatric illness	Elixhauser measure
Depression diagnoses	ICD-9 Depression Codes e.g., 296.2-296.36; 293.83; 309.0.
Anxiety Disorders/ PTSD diagnoses	ICD-9 CM codes for Anxiety and Stress-related conditions e.g., 293.84; 309.24; 309.28; 309.81; 300.00-300.09.
Serious Mental Illness diagnoses	ICD9-CM codes for Bipolar Affective Disorder Type 1, Schizophrenia e.g., 293.81-293.83; 296.40-296.7; 295.40-295.90; 296.56-293.83.

Alcohol/Substance Use Disorder Diagnoses	ICD9-CM codes for Alcohol, Amphetamine, Cocaine, Inhalant Use Disorders: 291.89-304.40.
Depression severity	PHQ-9 items and scores
Depression chronicity	Time from first to last ICD9 code or time between elevated PHQ9s
Anxiety severity	GAD-7 items and scores
PTSD severity	PCL-5 items and scores
Affective characteristics	PCL-5 clusters C (emotional avoidance), D (negative mood and cognitions), E (arousal and reactivity)
Somatic difficulties	Somatic factor of the PHQ9 (e.g., fatigue, sleeping difficulties)
Instrumental Variables	
Distance to the VA	e.g., GIS tracking, zip code mapping
System approachability	Is the mandatory annual depression screen completed in the past year?; Does pt have PCMH routine check in over the past two years?
Ability to reach VA	Has available transportation/eligible for VA transportation; full time or multiple jobs
Family support	Asian and Black race (as proxy) have been associated with increased social stigma of mental illness, including lack of family/friends support to seek mental health services
Beliefs about care	Gender and race have been associated beliefs about MH care
Unobserved Variables	
Transportation availability	These variables have been repeatedly identified in the literature as barriers to mental health treatment. We will not have this information available in the structured data.
Employment	
Child or family care	
Outcome Measure (Dependent Variable)	
Treatment initiation	A primary or secondary stop code showing a visit in mental health (with a psychologist or psychiatrist) or primary care AND an ICD9 for depression diagnosis.

Sampling plan and data extraction and processing:

**Data source and cohort selection.** We will use data from the VA Corporate Data Warehouse (CDW), a centralized data repository which contains electronic medical records of all Veteran patients who receive care through the VHA. The patient cohort (N = 88,456) used for completion of Aim 1 includes 1) OEF/OIF Veteran patients with a PHQ9  $\geq$ , 2) who were not already in treatment for depression prior to this PHQ9 assessment, 3) were never diagnosed with bipolar, personality, psychotic, and pervasive developmental disorders to be consistent with the National Committee on Quality Assurance measure of quality of care, HEDIS (HEDIS, 2018), as well as substance dependence or patients who are in treatment for substance related disorders at the time of recruitment. The exclusion criteria are based on the fact that the presence of these disorders may result in divergent treatment practices compared to unipolar depression in the absence of these conditions. Our primary outcome, treatment initiation, is conceptualized as a combination of service encounters with specialty mental health (psychologists, psychiatrists) or primary care providers charted into the patients' VHA medical records (excluding assessments) that were associated with any depressive disorder diagnosis. Our data are already IRB exempt, R&D and DART approved, and have already been extracted.

**Data processing.** Data will be initially checked for out of range values and missing data where appropriate through plotting and descriptive analyses. Data will be transformed as needed. Logistic regression is relatively free of restrictions and can accommodate a mix of predictors (continuous, discrete, dichotomous) (Tabachnick & Fidell, 2007). *With continuous predictors, the assumption is that there is a monotonic relationship (increase or decrease) between the predictor variable and odds of the binary outcome (i.e. engagement or lack of engagement in care). The functional of this linear assumption can be evaluated by use categorical indicator variables as well as transformations of the continuous variable, such as a quadratic form. Multicollinearity will be tested using two approaches. First, we will explore correlations among IVs and exclude variables based on high correlations ( $> .65$ ). Second, we will examine the size of the standard error (SEs) relative to the beta coefficient for each predictor in the model. Large SEs will be indicative of potential multicollinearity. Residuals will be tested to identify possible outliers.*

Analysis plan:

**Modeling risk for lack of treatment engagement.** For all analyses, lack of treatment engagement is the main dependent variable and will be investigated using three related definitions based on the date in which a PHQ9 score  $\geq 10$  is identified in the EHR. Specifically, we will examine whether treatment is initiated within 3-months, 6-months, or 12-months from the date of the PHQ9 assessment. *Independent variables of interest will be extracted based on proposed framework, empirical evidence, and availability in the EHR (see Table 1), including insight from a select number of semi structured surveys collected prior to data analysis (described below).*

*Fortunately, the EHR is rich in terms of wealth of potential predictors to carry out the analyses. This work is a first step in the development of an automated system that can be implemented in the VHA EHR to more easily identify patients who may be in need but at risk for lack of engagement in mental health treatment.* A direct logistic regression will be performed to evaluate the battery of proposed and potential factors as possible predictors of lack of treatment engagement. The final model will be estimated using the validation sample (half of our overall available sample). Regression (beta) coefficients and odds ratios will be extracted for interpretation and evaluation of risk to not engage in treatment in our next step.

*Computation of health service utilization risk score.* Using coefficients extracted from final logistic regression testing the best fitting patient phenotype associated with lack of treatment engagement, we will compute a risk score for lack of treatment engagement. This score will be used to select high risk patients enrolled in our intervention development and evaluation studies (Aims 2 and 3). The logistic regression equation will be used to calculate the risk scores using the intercept and co-variated specific coefficients that relate to the probability of lack of treatment initiation. Therefore, the equation will be based on the logistic regression model which will be developed in the log odds scale.

*Machine learning process.* This step of the data analysis will be conducted to assess the extent to which machine learning methods can potentially improve upon the prediction accuracy derived from the conventional logistic regression analysis. As with the conventional logistic regression analysis, the cohort of 88,456 OEF/OIF Veterans will be used. A range of machine learning methods will be used to compare results on variable importance and interpretability, with the goal of providing insight for clinicians on potential risk mitigation strategies for veterans at risk of not engaging in treatment for depression. The methods to be compared will include Lasso penalized logistic regression (Tibshirani 1996), random decision forests (Liaw 2002), decision trees (Hastie 2009), and support vector machines (Hastie, 2001). Each approach offers potential pros and cons in terms of modeling complex data and in interpretation. For example, decision trees accommodate high dimensions, model non-linear relationships, and perform well with missing data and are highly interpretable by humans. Support vector machines provide automated scaling of predictor variables and support linear and polynomial kernels for model training. Regardless of the method used, to prevent overfitting, 10-fold cross validation will be employed. This process splits the data into ten separate sets and builds a model on each set using the other nine sets. Variance across the ten models will be examined to evaluate model stability. Model performance will be evaluated using the standard F-Measure which is the harmonic mean of precision and recall. This will be augmented with use on metrics of predictive performance including area under the curve (AUC), sensitivity, and specificity, with a focus on clinical interpretability. Error analysis will be employed to improve model performance on 10 separate samples until model performance is maximized on the test set and then validated on the final set. As models are being developed, pruning algorithms will be used to make the model more generalizable. Finally, although there are no specific guidelines or power analysis for the determination of the exact sample size needed for specific models, generally samples such as  $n > 1000$  have been found to be adequate for machine learning. Our sample for this step of the analysis will be  $N = 88,456$  and we will be using the sample to its fullest. Therefore, we propose to use 10 ( $n = \sim 7000$ ) samples as training sets to test and fine-tune our phenotype model. We will use 2 additional ( $n = \sim 9000$ ) samples to do a final model testing and finally validate the model.

*Steps to control for unobserved variables.* Importantly, the logistic regression and machine learning methods described above are based on analyses of observed and instrumental variables that will be present in the VA CDW for OEF/OIF veterans. While these methods are established and generally well supported, there exists the possibility that some important “unobserved” variables will not be in the dataset for analysis. In this circumstance, the prediction equations may be suboptimal not only in terms of precision (lack thereof) due to missing variables, but also potential incorrect attribution of observed variables as being highly predictive of the decision to engage or not engage in depression care when, in fact, the observed variable is directly attributed to (caused by) a proximal unobserved variable.

Instrumental variable (IV) analysis is one of the methods used to: (1) counteract issues with measurement error in explanatory (observed) variables which result from a lack of accurate information available for analysis and (2) overcome the issue of omitted variables (Angrist & Krueger, 2001; Greenland, 2000). Identification of an appropriate “instrument” (e.g. actual travel time for the veteran from home to treatment facility) that addresses the potential bias from inaccurately measured and unobserved variables is often challenging. This circumstance in difficulty in being able to a priori identify appropriate IVs is anticipated for the present analysis. Therefore, to address unobserved selection bias we propose an evaluation of multiple methods prior to the initiation of data extraction and modeling: (1) conduct a semi-structured survey combining questions based on literature on environmental and system barriers and an open ended question inviting Veterans to provide feedback on any

other barriers that were not gleaned from the literature (see Appendix 3). Such an instrument will help us identify possible instrumental variables and unmeasured unobserved variables. (2) If warranted, IV analysis will also be used to test alternative models. Semi-structured surveys will be completed by 10 patients the PI has access to in the primary care clinic that meet our inclusion criteria (see Table 2) and that were referred to mental health services but missed their appointment based on EHR. (3) Empirical results from the development and validation analyses (described above) will be reviewed. First, if the ROC analysis indicates suboptimal model fit (e.g. AUC <0.8), this alone will suggest that important variables (whether observed or unobserved) were not included in the models. However, assuming overall good model fit (e.g. AUC  $\geq 0.8$ ), the next step will be to assess both “concordant” and “discordant” results. This analysis will again be based on semi structured surveys with 10 veterans who did or did not engage in treatment for depression.

To illustrate, each veteran in the analysis will have both an observed and predicted outcome score (i.e. engagement in treatment). For the “discordant” analysis, a random sample of 5 veterans who had very high predicted scores for engagement in treatment, yet did not engage in treatment, will be asked to complete our semi-structured survey. Emphasis will be on identifying the principal reason(s) for which the veteran did not engage in care despite having a very high predicted engagement score. Similarly, a random sample of 5 veterans who had very low predicted scores for engagement in treatment, yet engaged in treatment, will be asked to identify the reasons that influenced their decision to engage in treatment. For the “concordant” analysis, a random sample of 10 veterans who engaged or did not engage in treatment consistent with their predictive score will complete a semi-structured survey. In this circumstance, emphasis will be on comparing the extent to which rank ordering of the strength of the observed variables (predicted) in the prediction models actually reflected the treatment engagement decision making process employed by the veteran. This qualitative information will provide insight into to validity of the variables used in the prediction models, and again, whether important unobserved variables influenced the veteran’s decision for treatment engagement.

Next, I will conduct a 2-phase intervention development and formative evaluation process. Phase 1 entails formative development using a human-centered design completed in **Aim 2**. Phase 2 entails formative evaluation using mixed-methods completed in **Aim 3**. The two aims will be achieved using two separate samples (Aim 2, n = 10; Aim 3, n = 15). Findings from Aim 1 will be used to select and recruit patients for Aims 2-3. See the Human Subjects section for safety concerning using an asynchronous tool to collect mental health status.

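### Table 1's substance-use code range, read literally, contains 8 of the 12 depression, anxiety/PTSD and serious-mental-illness entries in the same table, so the written predictor is not specific to substance use

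*Protocol*

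**What the plan says.** Table 1 in Protocol section A4a lists the variables for Aim 1. Its four psychiatric diagnosis rows are:

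- Depression: "ICD-9 Depression Codes e.g., 296.2-296.36; 293.83; 309.0".
- Anxiety/PTSD: "ICD-9 CM codes for Anxiety and Stress-related conditions e.g., 293.84; 309.24; 309.28; 309.81; 300.00-300.09".
- SMI: "ICD9-CM codes for Bipolar Affective Disorder Type 1, Schizophrenia e.g., 293.81-293.83; 296.40-296.7; 295.40-295.90; 296.56-293.83".
- Alcohol/substance use: "ICD9-CM codes for Alcohol, Amphetamine, Cocaine, Inhalant Use Disorders: 291.89-304.40".

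The first three rows mark their codes as examples. The substance-use row does not, and it gives a single span. Elsewhere in these rows semicolons separate list items and hyphens join the ends of a range.

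Table 1 feeds the models. Under the heading on modeling risk, the protocol says "Independent variables of interest will be extracted based on proposed framework, empirical evidence, and availability in the EHR (see Table 1"). The coefficients then become the risk score used to choose patients for Aims 2 and 3 (A4a, computation of the risk score; A4b, sampling plan). The outcome, treatment initiation, itself needs a depression code: a qualifying visit in mental health or "primary care AND an ICD9 for depression diagnosis".

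The cohort description separately excludes certain diagnoses, "as well as substance dependence or patients who are in treatment for substance related disorders at the time of recruitment". It gives no codes for any exclusion. The SAP mentions no diagnosis codes.

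**The concern.** A span from 291.89 to 304.40 crosses the part of the numbering in which the table places most of its other psychiatric codes. An analyst who built the substance-use flag from the row as printed would mark a patient with a 296.2-296.36 depression code as having a substance use disorder.

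The interpretation of Aim 1 is at stake. The substance-use flag would be partly a second depression flag under another name, so neither its odds ratio nor its machine-learning importance would describe substance use. The protocol wants these results to give clinicians insight into how to reduce the risk of non-engagement, and it carries the coefficients into recruitment for the later aims. A wrong label on a predictor would mislead the first use and could distort the second.

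The SMI row has two further faults. Its last range has a lower end point larger than its upper one, and it shares 293.83 with the depression row.

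**Working it through.** There is no derived figure in the plan to reproduce. The check is whether each listed entry lies inside the substance-use range.

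Inputs: the range [291.89, 304.40] and the 12 entries in the depression, anxiety/PTSD and SMI rows, all from Table 1.

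Rule: an entry from a to b is inside if 291.89 ≤ min(a, b) and max(a, b) ≤ 304.40. For a single code, a = b. Taking the minimum and maximum means the backwards SMI range is read from low to high.

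| Row | Entry | Inside 291.89-304.40? |
|---|---|---|
| Depression | 296.2-296.36 | Yes |
| Depression | 293.83 | Yes |
| Depression | 309.0 | No (above 304.40) |
| Anxiety/PTSD | 293.84 | Yes |
| Anxiety/PTSD | 309.24 | No |
| Anxiety/PTSD | 309.28 | No |
| Anxiety/PTSD | 309.81 | No |
| Anxiety/PTSD | 300.00-300.09 | Yes |
| SMI | 293.81-293.83 | Yes |
| SMI | 296.40-296.7 | Yes |
| SMI | 295.40-295.90 | Yes |
| SMI | 296.56-293.83 (backwards) | Yes, read as 293.83-296.56 |

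Totals: depression 2 of 3, anxiety/PTSD 2 of 5, SMI 4 of 4. Together 2 + 2 + 4 = 8 of 3 + 5 + 4 = 12.

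Checks on the SMI row:

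- 296.56 > 293.83, so the last range is empty if taken literally.
- Read low to high, it contains the main depression range, since 293.83 ≤ 296.2 and 296.36 ≤ 296.56. Simply swapping its ends would therefore put that depression range inside the SMI definition.
- 293.83 is a depression entry and also the upper end of the SMI range 293.81-293.83.

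These are counts of table entries, not of patients. The documents give no code frequencies, so the share of the 88,456 Veterans affected cannot be calculated.

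**The case against.** The strongest reply is that the row names alcohol, amphetamine, cocaine and inhalant use disorders, and that those words limit the codes meant. The hyphen would then be shorthand for the first and last items of a discrete list. In addition, the protocol says the data have already been extracted, so the query may have used a correct list. Both points stand as limits: the documents show a faulty written definition, not a misclassified dataset. They do not make the definition reproducible, because the row lists no individual codes and hyphens mark ranges elsewhere in these rows.

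A second reply is that some of the overlap hardly matters. The cohort excludes anyone ever diagnosed with bipolar or psychotic disorder, so many codes in the four SMI entries should be rare in it. That is fair. It leaves the two depression and two anxiety/PTSD entries, and depression is the overlap that matters most here.

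A third is that the plan's data-processing step excludes variables correlated above .65. This is a partial safeguard at best. It might remove either the depression or the substance-use variable without revealing why, and a lower correlation would leave the mislabelled flag in the model.

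Two stronger readings are tempting, and the documents support neither:

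- A reader might infer that the range turns the substance-use flag into a stand-in for the outcome, since the outcome requires a depression code. But depression diagnoses are already a listed predictor, so predictors and outcome share codes whatever the substance-use row says. The outcome also needs a qualifying visit, and the plan does not date the diagnosis predictors relative to the PHQ9.
- A reader might infer that the range removes the target patients through the substance exclusion. The exclusion cites no codes and does not refer to Table 1. The preliminary studies section also says that the data to be reused for Aim 1 have already supported an analysis of treatment initiation, which fits poorly with a cohort stripped of most of its listed depression codes.

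**Conclusion.** The point holds as a fault in a written variable definition. Read literally, the substance-use range takes in 8 of the 12 entries in the other three psychiatric rows, including two of the three depression entries. A predictor built that way would overlap the depression predictor and could not be interpreted as substance use, in the logistic risk score or in the machine-learning comparison. The backwards SMI range and the double listing of 293.83 are definite errors on the page.

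This rests on reading the hyphen as a range, as in the neighbouring rows. It does not rest on any claim about what was extracted, and the effect on the models is unknown. The reach is Aim 1 and, through the risk score, selection into Aims 2 and 3; the SAP's own analyses use no diagnosis codes. The definition should be corrected before the models are fitted, mainly because doing so is cheap.

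**What to change.** In Table 1:

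1. Replace the single span with an explicit list of codes for each named substance use disorder.
2. Correct the backwards SMI range by stating the codes intended, not merely by swapping its ends.
3. Assign 293.83 to either the depression or the SMI row.
4. Check by program that no code appears in more than one diagnosis row.
5. Compare the corrected lists with the extraction code, and re-derive any flag that differs before fitting the Aim 1 models.

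The cost is an edit to one table, a short overlap check and, if the extraction followed the printed range, re-derivation of the affected flags from data that the protocol says are already held. No new data collection is needed for this.
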